11.2 Database management and quality control

Novartis personnel (or designated CRO) will review the data entered by investigational staff for completeness and accuracy. Electronic data queries stating the nature of the problem and requesting clarification will be created for discrepancies and missing values and sent to the investigational site via the EDC system. Designated investigator site staff are required to respond promptly to queries and to make any necessary changes to the data.

Concomitant treatments and prior medications entered into the database will be coded using the WHO Drug Reference List, which employs the Anatomical Therapeutic Chemical classification system. Medical history/current medical conditions and adverse events will be coded using the Medical dictionary for regulatory activities (MedDRA) terminology.

At the conclusion of a non-IRT study, the occurrence of any emergency code breaks will be determined after return of all code break reports and unused supplies to Novartis.

Once all the necessary actions have been completed and the database has been declared to be complete and accurate, it will be locked. Any changes to the database after that time can only be made after written agreement by Novartis development management.

Commercially Confidential Information

11.3 Site monitoring

Before study initiation, at a site initiation visit or at an investigator's meeting, a Novartis or delegated CRO representative will review the protocol and data capture requirements (i.e. eSource DDE or eCRFs) with the investigators and their staff. During the study, Novartis employs several methods of ensuring protocol and GCP compliance and the quality/integrity of the sites' data. The field monitor will visit the site to check the completeness of subject records, the accuracy of data capture / data entry, the adherence to the protocol and to Good Clinical Practice, the progress of enrollment, and to ensure that study treatment is being stored, dispensed, and accounted for according to specifications. Key study personnel must be available to assist the field monitor during these visits. Continuous remote monitoring of each site's data may be performed by a centralized Novartis or delegated CRO, CRA organization. Additionally,

a central analytics organization may analyze data & identify risks & trends for site operational parameters, and provide reports to Novartis clinical teams to assist with trial oversight.

The investigator must maintain source documents for each subject in the study, consisting of case and visit notes (hospital or clinic medical records) containing demographic and medical information, laboratory data, electrocardiograms, and the results of any other tests or assessments. All information on CRFs must be traceable to these source documents in the subject's file. The investigator must also keep the original informed consent form signed by the subject (a signed copy is given to the subject).

The investigator must give the monitor access to all relevant source documents to confirm their consistency with the data capture and/or data entry. Novartis monitoring standards require full verification for the presence of informed consent, adherence to the inclusion/exclusion criteria, documentation of SAEs, and of data that will be used for all primary variables. Additional checks of the consistency of the source data with the CRFs are performed according to the study-specific monitoring plan. No information in source documents about the identity of the subjects will be disclosed.

12 Data analysis and statistical methods

The study analysis will be conducted on all patient data at the time the trial ends. As this is a multi-period study, all listings will include both study day and period day, especially when early escalation entails moving into a period earlier than on the standard study day. Statistical summaries and figures will also be aware of the same distinction where relevant.

Any data analysis carried out independently by any investigator should be submitted to Novartis before publication or presentation.

12.1 Analysis sets

For all analysis sets, patients will be analyzed according to the study treatments received.

The Full Analysis Set (FAS) comprises all patients that received any study drug.

The safety analysis set will also include all patients that received any study drug and hence is not referred to again.

The PK analysis set will include all patients with at least one available valid (i.e., not flagged for exclusion) PK concentration measurement, who received any study drug and with no protocol deviations that impact on PK data.

Commercially Confidential Information

12.2 Subject demographics and other baseline characteristics

Demographic and other baseline data, including disease characteristics, will be listed and summarized descriptively by treatment sequence for the full analysis set.

Categorical data will be presented as frequencies by treatment sequence. For continuous data, mean, standard deviation, median, minimum, and maximum will be presented.

Relevant medical histories and current medical conditions at baseline will be summarized by system organ class and by preferred term, by treatment sequence for all patients.

12.3 Treatments

The full analysis set will be used for the analyses below. Categorical data will be summarized descriptively as frequencies. For description of continuous data, mean, standard deviation, median, minimum, and maximum will be presented.

The duration of exposure in days (including half days) to each dose of LNP023 will be summarized by means of descriptive statistics.

Concomitant medications and significant non-drug therapies prior to and after the start of the study treatment will be listed and summarized according to the Anatomical Therapeutic Chemical (ATC) classification system, by treatment sequence group.

12.4 Analysis of the primary endpoint(s)

12.4.1 Definition of primary endpoint(s)

The primary efficacy endpoint for assessing the effect of LNP023 is response rate, where a patient will be considered a responder if LDH is below ULN or the percentage reduction from baseline in serum LDH is at least 60% at any time up to and including Week 12 for that patient, whether or not

Commercially Confidential Information

12.4.2 Statistical model, hypothesis, and method of analysis

There is no statistical model for the primary endpoint apart from observing and counting success or failure for each patient. For the purposes of this study a positive sign of efficacy is when the estimated response rate is at least 50%. For example, this criterion will be met when at least 5 out of 10 patients in the overall study, or 3 of 5 in one of the two Cohorts are considered responders.

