| q.d. | Quaque die (once a day) |

Commercially Confidential Information

| | |
|-------|--|
| QTcF | Fridericia QT correction formula |
| REP | Roll-over extension program |
| RBC | red blood cell(s) |
| SAE | serious adverse event |
| sCR | serum creatinine |
| SD | standard deviation |
| SoC | Standard of Care |
| SOM | Site Operations Manual |
| SUSAR | Suspected Unexpected Serious Adverse Reactions |
| TSH | Thyroid stimulating hormone |
| ULN | upper limit of normal |

Commercially Confidential Information

| | |
|-------|----------------------------------|
| WBC | white blood cell(s) |
| WHO | World Health Organization |
| WoC | Withdrawal of Consent |
| WOCBP | Women of child bearing potential |

Glossary of terms

| | |
|-------------------------------|--|
| Assessment | A procedure used to generate data required by the study |
| Cohort | A specific group of subjects fulfilling certain criteria |
| Control drug | Any drug(s) (an active drug or an inactive drug, such as a placebo) which is used as a comparator to the investigational drug being tested in the trial |
| Dosage | Dose of the study treatment given to the subject in a time unit (e.g. 100 mg once a day, 75 mg twice a day) |
| Electronic Data Capture (EDC) | Electronic data capture (EDC) is the electronic acquisition of clinical study data using data collection systems, such as Web-based applications, interactive voice response systems and clinical laboratory interfaces. EDC includes the use of Electronic Case Report Forms (eCRFs) which are used to capture data transcribed from paper source forms used at the point of care. |
| Enrollment | Point/time of subject entry into the study at which informed consent must be obtained (i.e. prior to starting any of the procedures described in the protocol) |
| Epoch | Interval of time in the planned conduct of a study. An epoch is associated with a purpose (e.g. screening, randomization, treatment, follow-up) which applies across all arms of a study. |
| eSource | eSource Direct Data Entry (DDE) refers to the capture of clinical study data electronically, at the point of care. eSource combines source documents and case report forms (eCRFs) into one application, allowing for the real time collection of clinical trial information to sponsors and other oversight authorities, as appropriate. |
| Healthy volunteer | A person with no known significant health problems who volunteers to be a study participant |

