|--------------------------|--|
| Other assessments | Commercially Confidential Information |
| Data analysis | 
The primary efficacy variable for assessing the effect of LNP023 is response rate; where a patient will be considered a responder if LDH is below ULN or the percentage reduction from baseline in serum LDH is at least 60% at any time up to and including week 12 for that patient. In a proof of concept paradigm, a positive sign of efficacy is when the estimated response rate is at least 50%. For example, this criterion will be met when 5 out of 10 patients are considered responders.
 
Commercially Confidential Information
 |
| | 
The same mixed modelling approach will be used for other continuous response variables. Skewed data will be transformed in order to meet underlying normality and homoscedasticity assumptions. In case early escalation gives data only to two weeks for some patients, the modelling will be adjusted to suit.
 |
| Key words | PNH, hemolysis, LDH, hemoglobin |

1 Introduction

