At least 10 patients will be included in the study, as replacement can occur if any patient withdraws for reasons unrelated to safety or lack of efficacy.

Active hemolysis is defined by an LDH value \geq 1.5x ULN. At least 3 pre-treatment LDH measurements each separated by at least a week over a maximum of 8 weeks prior to study Day 1 of the study should be \geq 1.5x ULN, in order to include the patients in the study. LDH medical history data can be taken into consideration for inclusion purposes but at least one value must be from the study central laboratory. If medical history data is not available, the screening period may consist of several visits for LDH verification.

Total study duration from screening until EOS is approximately 28 months. This three-period study includes:

- a screening phase of up to 8 weeks,
- a baseline visit,
- Day 1 (first day that the investigational drug is given),
- a 4-week treatment period of LNP023 at the first dose in the assigned sequence (Period 1),
- an 8-week treatment period at the second dose in the assigned sequence (Period 2),
- an approximately 2 year treatment extension period for patients who respond to the LNP023 treatment (Period 3)
- taper down period of 2 weeks applicable only for patients discontinuing LNP023 treatment (Week 13 for non-responders or Week 109 for responders).

Commercially Confidential Information

- an EoS visit that will take place 1 week after the last LNP023 administration for patients not joining the roll-over extension program (REP). For patients joining the REP ([Section 9.2](#)), the last treatment visit will become the EoS visit.

A safety follow-up call 30 days after the last administration of LNP023 will be performed for patients not joining the REP.

Figure 3-1 Study design

Commercially Confidential Information

Patients will be randomized to sequence 1 or sequence 2 in ratio 1:1.

Commercially Confidential Information

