12.8 Sample size calculation

12.8.1 Primary endpoint(s)

With 10 subjects this study has 80% probability to meet the efficacy criteria of 5 or more successful patients out of 10 if the true response rate is 58%.

Commercially Confidential Information

13 Ethical considerations and administrative procedures

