#### 7.1.2 Descriptive analyses

Frequency tabulations reporting number and percentage of responders by week 12 by randomized sequence. Frequency tables will also be summarized by dose over time as described in [Section 4](#).

There is no statistical model for the primary endpoint apart from observing and counting success or failure for each patient. For the purposes of this study a positive sign of efficacy is when the estimated response rate is at least 50%. For example, this criterion will be met when at least 5 out of 10 patients in the overall study, or 3 of 5 in one of the two Cohorts are considered responders.

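### The primary success criterion, read literally, is met by 3 of 5 responders in one Cohort, but the stated 80% probability covers only the 5-of-10 rule

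*Protocol*

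**What the plan says.** Protocol 12.4.2 gives the primary endpoint no statistical model beyond counting responders. It sets the threshold as follows: "For the purposes of this study a positive sign of efficacy is when the estimated response rate is at least 50" per cent. It then illustrates how the threshold can be reached: "at least 5 out of 10 patients in the overall study, or 3 of 5 in one of the two Cohorts are considered responders". SAP 7.1.2 repeats both sentences and plans "Frequency tabulations reporting number and percentage of responders by week 12 by randomized sequence".

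Two other places describe the criterion without the Cohort clause:

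- The Data analysis entry of the protocol summary says: "For example, this criterion will be met when 5 out of 10 patients are considered responders".
- Protocol 12.8.1 says: "With 10 subjects this study has 80% probability to meet the efficacy criteria of 5 or more successful patients out of 10", for a true response rate of 58%.

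The visible text does not tie Cohort to a group in this trial. The glossary entry is generic: "A specific group of subjects fulfilling certain criteria". The only grouping that the visible design describes is by sequence: "Patients will be randomized to sequence 1 or sequence 2 in ratio 1:1" (Protocol Section 3).

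**The concern.** The rule that decides whether the study shows a positive sign is not the same in all the places that state it. In 12.4.2 and SAP 7.1.2 there are two routes joined by "or". In 12.8.1 there is one.

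The second route also sits badly with the 50% principle that it is meant to illustrate. Three of five is 60% within the Cohort. With no responders, or one, in the other five patients, it is only 30% or 40% of the study. The text does not say whether the 50% refers to the study or to the Cohort.

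This counting rule is the only visible pre-specified basis for calling the study positive, and the 80% is the only visible statement of how it performs. If the literal rule is the intended one, that statement describes a different and stricter rule. Nothing visible shows how often the looser rule would pass a drug with a modest response rate.

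**Working it through.** **Inputs.** 10 patients, at least 5 responders, true rate 58% (Protocol 12.8.1). Alternative route of 3 of 5 in one Cohort (Protocol 12.4.2, SAP 7.1.2). Allocation 1:1 to two sequences (Protocol Section 3). *Assumptions, not in the visible text:* Cohort means randomized sequence, there are 5 patients in each, and patients respond independently. The main case also takes the same true rate p in both sequences. I read 3 of 5 as at least 3 in at least one sequence. If both reach 3, the total is at least 6 and the overall branch is met anyway.

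**Step 1: the plan's own figure.** With X ~ Binomial(10, 0.58):

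P(X ≥ 5) = 1 − (0.00017 + 0.00236 + 0.01466 + 0.05398 + 0.13044) = 1 − 0.20161 = 0.798.

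The stated 80% reproduces, and it belongs to the 5-of-10 rule.

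**Step 2: what the either/or rule amounts to.** If neither sequence reaches 3, the total is at most 2 + 2 = 4. So 5 of 10 cannot be reached without 3 of 5 in at least one sequence, and the overall branch adds nothing. The outcomes that pass only through the Cohort clause are 3+0, 4+0 and 3+1, in either order: overall rates of 30%, 40% and 40%.

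**Step 3: its probability at 58%.** For one sequence:

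c = 10(0.58³)(0.42²) + 5(0.58⁴)(0.42) + 0.58⁵ = 0.3442 + 0.2376 + 0.0656 = 0.6475.

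For either sequence: 1 − (1 − c)² = 1 − 0.3525² = 0.876.

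The difference, 0.8757 − 0.7984 = 0.077, is the probability of the outcomes listed in Step 2.

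**Step 4: other true rates, same formulas.**

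| True rate in both sequences | 5 of 10 | Either/or |
|---|---|---|
| 20% | 3.3% | 11.2% |
| 30% | 15.0% | 30.0% |
| 40% | 36.7% | 53.4% |
| 50% | 62.3% | 75.0% |
| 58% | 79.8% | 87.6% |

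Solving for 80%: the 5-of-10 rule needs a true rate of about 58%, the either/or rule about 53%.

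**Step 5: unequal rates.** The two sequences need not have the same response rate. Enumerating all 36 outcomes for 5+5 patients:

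| True rates | Mean | 5 of 10 | Either/or |
|---|---|---|---|
| 68% and 48% | 58% | 80.4% | 89.8% |
| 78% and 38% | 58% | 82.2% | 94.7% |
| 40% and 20% | 30% | 14.4% | 35.7% |

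In these cases the gap is wider than with equal rates at the same mean.

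**The case against.** The best defence has four parts.

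- **12.8.1 is not wrong.** It names its rule, sample size and rate, and the result is correct. If the Cohort route also counts, 80% understates the chance of a positive sign at 58%. All of this stands. A reader might infer a sample-size error, and there is none. What remains is that the figure covers one of two routes, and that at low true rates the second route makes a positive sign easier to reach.
- **The wording is illustrative.** The summary, 12.4.2 and SAP 7.1.2 all say "for example", so leaving the second route out of the summary is not a contradiction in itself. That also stands. But 12.8.1 is not an example: it presents 5 of 10 as the efficacy criteria.
- **The study is non-confirmatory.** No null rate or alpha is stated, and responders are tabulated by sequence, so a 3/5 and 0/5 result would be visible. This limits the consequence to the label attached to the result. A reader might infer inflated type I error from two routes to success. The documents set no error rate to breach.
- **Redaction.** Confidential blocks follow the 80% sentence in 12.8.1 and the randomization sentences, and they cover the interim-analysis text and most of SAP Section 4. Any of these may define Cohort or give a Cohort-level probability, so an undefined term or a missing calculation cannot be charged to the plan. The point therefore rests only on the mismatch between visible sentences.

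A reader might go further in two ways. One is to say that the plan leaves open whether 3 of 5 counts at all. The text says that the criterion will be met by it, so the literal reading is that it does. The other is to compute larger gaps for unequal sequence sizes, since the study takes at least 10 patients and allows replacement. Those figures need thresholds for groups of other sizes, which the documents do not give.

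**Conclusion.** The point holds as a mismatch in visible text. The literal criterion in Protocol 12.4.2 and SAP 7.1.2 accepts 3 of 5 in one Cohort, which can mean 30% or 40% overall. The 80% in 12.8.1 applies only to 5 of 10.

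With equal rates, the gap is about 8 points at a true 58%. It is about 8, 15 and 17 points at 20%, 30% and 40%, where the looser rule multiplies the chance of a positive sign by about 3.4, 2.0 and 1.5. These sizes rest on Cohort meaning sequence and on 5+5 patients.

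No estimate or planned analysis changes. What changes is which results may be called positive. It is worth fixing because this is the primary decision rule. Confidence is medium because of the redactions.

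**What to change.** Use one study-level rule in the protocol summary, 12.4.2, 12.8.1 and SAP 7.1.2.

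**Preferred:** make an overall response rate of at least 50% (5 of 10) the single criterion. The existing 80% already describes it. Report 3 of 5 within a sequence descriptively, and replace "Cohorts" with "sequences" if that is what is meant.

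**If either/or is intended:** keep it, state it in all four places, and restate 12.8.1 as about 88% at a true 58% (80% at about 53%) for 5+5 patients and equal rates. Add the chance of a positive sign at true rates of 20%, 30% and 40%: about 11%, 30% and 53%. Say what applies if the sequences do not have 5 patients each.

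The cost is about one sentence in each place. The first option lowers the chance of a positive sign by about 8 points at 58% if either/or was the intention. The second accepts that a study with 3 or 4 responders out of 10 can be called positive.

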12.4.3 Handling of missing values/censoring/discontinuations

For calculation of the success rate for the primary endpoint all patients enrolled in the study apart from those who were replaced for reasons other than safety or efficacy will be included in the denominator.

Commercially Confidential Information

12.5 Analysis of secondary endpoints

Assessment of plasma pharmacokinetics is a secondary endpoint but the analyses for it are described below in [Section 12.5.3](#). Assessing the dose-response effect on LDH and other parameters associated with PNH associated hemolysis is the first secondary objective.

Mixed effect modelling will be performed for LDH.

Commercially Confidential Information

Commercially Confidential Information

Baseline LDH will be calculated as the average of the last three screening values prior to randomization. The subject term will be considered as random so as to allow recovery of between subject information.

Commercially Confidential Information

The same mixed modelling approach will be used for other key continuous response secondary endpoint variables apart from LDH that are markers of intravascular and extravascular hemolysis, or are markers of thrombosis, as well as for PK parameters excluding Tmax (see [Section 12.5.3](#)). In these cases, except for PK parameters, the baseline covariate is the average of all pre-treatment values.

Data may be transformed in order to meet underlying normality and homoscedasticity assumptions. In case early escalation gives data only to two weeks for some patients, the modelling will be adjusted to suit, in the first instance looking only at Week 2 data for all patients.

12.5.1 Handling of missing values/censoring/discontinuations

Commercially Confidential Information

12.5.2 Safety endpoints

For all safety analyses, the full analysis set will be used.

Commercially Confidential Information

Safety summaries (tables, figures) include only data from the on-treatment period with the exception of baseline data which will also be summarized where appropriate (e.g., when change from baseline is used). In addition, a separate summary for any deaths including on treatment and post treatment deaths will be provided. In particular, summary tables for adverse events (AE) will summarize only on-treatment events.

The on-treatment period lasts from the date of first administration of study treatment to 30 days after the date of the last actual administration of any study treatment.

Adverse events

All information obtained on adverse events will be displayed as described above taking into account the study design involving sequences,

Commercially Confidential Information

Listings will be down to patient level. The number (and percentage) of patients with treatment

emergent adverse events (events starting after the first dose of study medication or events present prior to start of double-blind treatment but increased in severity based on preferred term) will be summarized in the following ways:

- by treatment dose group including split by first and second four weeks in second period, primary system organ class and preferred term.

Commercially Confidential Information

Separate summaries will be provided for study medication related adverse events, death, serious adverse events, other significant adverse events leading to study and/or investigational drug discontinuation and any adverse events leading to dose adjustment.

A subject with multiple adverse events within a primary system organ class is only counted once towards the total of the primary system organ class. Adverse events which will be counted for a specific treatment period are those which are treatment-emergent. These events are those with an onset after the start of the dose level treatment period, or which were present prior to the start of the treatment period but increased in severity, changed from being not suspected to being suspected of study drug relationship, or developed into SAEs after the start of the dosing period.

Vital signs

All vital signs data will be listed by sequence, treatment dose group, subject, and visit/time and if ranges are available, abnormalities (and relevant orthostatic changes) will be flagged. Summary statistics will be provided as described above. Individual overlaid profile plots over time with current dose level per patient color-coded will be presented.

12-lead ECG

PR, QRS, QT, QTcF, and RR intervals will be obtained from 12-lead ECGs for each patient during the study. ECG data will be read and interpreted locally.

All ECG data will be listed by sequence, treatment dose group, subject and visit/time. Abnormalities will be flagged. Summary statistics will be provided as described above. Individual overlaid profile plots over time with current dose level per patient color-coded will be presented.

Clinical laboratory evaluations

All laboratory data will be listed by sequence, treatment dose group, subject, and visit/time and if normal ranges are available abnormalities will be flagged. Summary statistics will be provided as described above. Individual overlaid profile plots over time with current dose level per patient color-coded will be presented.

Other safety evaluations

All transfusion and patient diary data will be listed by sequence, treatment dose group, subject, and visit/time and relevant descriptive summaries will be formed.

